4.3.2.4. Sensitivity Analysis Related to Treatment Regimen Estimand

For submission of Study GPHM to the US FDA tirzepatide application for chronic weight management, additional sensitivity analyses of the primary efficacy outcomes will be conducted using the FAS and guided by treatment-regimen estimand, which represents the efficacy irrespective of adherence to study drug. This assessment will analyze percent change in body weight obtained at the 72-week visit using an ANCOVA and the percentage of participants achieving at least 5% body weight reduction obtained at the 72-week visit using a logistic regression model. The terms for both models will be the same as specified in Section 4.3.2.1. These analyses are intended to assess the robustness of primary efficacy results using different missing data imputation methods.

- Retrieved dropout multiple imputation: missing values of change in body weight at the 72-week visit will be imputed based on observed body weight change from randomization values at the visit from participants in the same treatment group who had their efficacy assessed after early discontinuation of study drug. In cases where there are not enough retrieved dropouts to provide a reliable imputation model (for example, the model implemented by the SAS program does not converge), the placebo multiple imputation method (described below) will be used.

- Placebo multiple imputation: missing values of change in body weight at the 72-week visit will be imputed based on observed body weight change from baseline values at the visit from participants in the placebo treatment group.
- Return to baseline imputation: missing values of body weight at the 72-week visit will be imputed using the return-to-baseline multiple imputation method to account for within subject variability (Qu and Dai 2022).

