4.3.2.3. Methods for Hybrid Imputations

For efficacy analyses relative to the treatment regimen estimand, the ICEs and the resulting missing values will be handled as follows:

- **Category 1** - For missing data solely due to exceptional circumstances, such as pandemic or natural disasters (after other reasons for missing data are ruled out), missing data are considered as missing at random. The missing data will be imputed using all non-missing data of the primary outcome measurement from the same treatment arm.
- **Category 2** - For missing data due to all other ICEs, missing data will be imputed based on retrieved dropouts in the same treatment arm, defined as observed primary outcome measurements, from participants in the same treatment group who had their efficacy assessed after ED of study drug. In cases where there are not enough retrieved dropouts to provide a reliable imputation model (for example, the model implemented by the statistical analysis software [SAS] program does not converge), an alternative multiple imputation method referencing the placebo group (that is, placebo multiple imputation) will be used.

In cases where placebo multiple imputation method is used for missing data imputation in Category 2 due to not enough retrieved dropouts, the missing data in Category 1 will be imputed using all nonmissing data of the primary outcome measurement from the placebo group.

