4.9. Changes to Protocol-Planned Analyses

To provide data on efficacy of the investigational product that would be valuable to better inform clinical decisions in management of people living with obesity, protocol-planned objectives are changed as below.

Key Secondary Objectives

- added the key secondary objective, “QW tirzepatide MTD is superior to placebo for proportion of participants who achieve $\geq 20\%$ body weight reduction from randomization to 72 weeks”

Additional Secondary Objectives

- added the additional secondary objective, “Compare QW tirzepatide MTD with placebo for mean change in Non-HDL-cholesterol (mg/dL) from randomization to 72 weeks”

Subgroup Analysis for Primary Analysis

- added the subgroup variable, “region of enrollment (US, outside of US)” for both outcome measures

5. Sample Size Determination

Approximately 1100 participants will be screened, and 800 participants will be enrolled into the 12-week lead-in period in order to achieve approximately 600 participants randomly assigned to study drug intervention (300 participants per treatment group).

The sample size determination assumes that evaluation of superiority of tirzepatide MTD (10 mg or 15 mg) to placebo will be conducted at a 2-sided significance level of 0.05 using a 2-sample t-test. Additionally, a difference of at least 12% in mean body weight percentage reduction from randomization at 72 weeks for tirzepatide MTD compared to placebo, a common SD of 10%, and a dropout rate of 25% are assumed for statistical power calculations. Under the assumptions above, randomizing 600 participants in a 1:1 ratio to MTD (300 participants) and placebo (300 participants) provides more than 90% power to demonstrate superiority of tirzepatide MTD to placebo.

The chosen sample size and randomization ratio also provides >90% power to establish superiority of tirzepatide MTD to placebo in terms of proportion of participants achieving at least 5% body weight reduction from randomization at 72 weeks, based on a Chi-square test at a 2-sided significance level of 0.05, assuming 20% of placebo-treated participants and 46% of tirzepatide-treated participants achieve the goal and a dropout rate of 25%.

6. Supporting Documentation

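### If retrieved dropouts are too few, two of the three treatment-regimen sensitivity analyses repeat the primary analysis, and the third gives the same expected mean difference when missingness is balanced.

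*SAP*

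**What the plan says.** For the treatment regimen estimand, SAP 4.3.2.3 sorts missing Week 72 weights into two categories. Category 1 (missing solely because of exceptional circumstances) is imputed from the same arm. Category 2 (all other reasons) is imputed from retrieved dropouts in the same arm. If there are not enough of these, then for Category 2 "an alternative multiple imputation method referencing the placebo group (that is, placebo multiple imputation) will be used". In that case Category 1 moves as well: "the missing data in Category 1 will be imputed using all nonmissing data of the primary outcome measurement from the placebo group". Non-convergence is given only as an example of too few; no minimum number is stated.

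SAP 4.3.2.4 lists three sensitivity analyses of both co-primaries, on the FAS and with the model terms of 4.3.2.1:

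1. Retrieved-dropout imputation. If retrieved dropouts are too few, "the placebo multiple imputation method (described below) will be used".
2. Placebo multiple imputation.
3. Return-to-baseline multiple imputation.

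Their purpose is stated: "These analyses are intended to assess the robustness of primary efficacy results using different missing data imputation methods". No delta-adjusted or tipping-point analysis is listed.

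**The concern.** A sensitivity analysis is informative only if it changes the assumption about the missing values. The fallback is reached when few participants were weighed after stopping drug, which is when the imputation assumption has least data behind it. In that situation the plan's set of different methods shrinks, because two members adopt the assumption the primary has just adopted. A reader would see agreement between analyses that are the same by construction. The one remaining method would agree with them on the mean whenever missingness happens to be balanced, whatever the missing weights really were. The plan would then not report how wrong the assumption would have to be before either co-primary result failed.

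**Working it through.** **Inputs** (SAP Section 5): "a difference of at least 12% in mean body weight percentage reduction from randomization at 72 weeks"; "a common SD of 10%, and a dropout rate of 25% are assumed for statistical power calculations"; 300 per arm; two-sided 0.05; responder rates of 20% on placebo and 46% on tirzepatide.

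**Assumptions.** The 25% dropout is used as the share of missing Week 72 weights in each arm; Visit 99 may make it lower. The placebo mean change mP is not given, so -5 to +5 is used. Return-to-baseline values are taken as centred on zero change from randomization.

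**Plan's own figure.** With 300 x 0.75 = 225 per arm, power is above 99.9% for the means and 99.998% for the proportions, so the stated power above 90% reproduces.

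**Step 1: what each analysis imputes under the fallback.**

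| Analysis | Category 1 | Category 2 |
|---|---|---|
| Primary | placebo data | placebo MI |
| Sensitivity 1 | placebo MI | placebo MI |
| Sensitivity 2 | placebo MI | placebo MI |
| Sensitivity 3 | return to baseline | return to baseline |

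The first three rows are one analysis, apart from random imputation noise. This reads placebo multiple imputation as one method in both sections.

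**Step 2: the mean.** Let dT and dP be the missing shares, and mT and mP the observed means.

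- Placebo MI: (1 - dT)mT + dT·mP - mP = (1 - dT)(mT - mP).
- Return to baseline: (1 - dT)mT - (1 - dP)mP.
- Return to baseline minus placebo MI: mP(dP - dT).

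With 25% missing in both arms, each gives 0.75 x (-12) = -9.0 for any mP; with 10% missing, each gives -10.8. Simulation (300 trials per setting, 30 imputations, ANCOVA, Rubin's rules) agrees at 25%: -9.02 and -9.02 for mP = 0; -8.93 and -8.95 for mP = +3; -9.01 and -9.03 for mP = -3.

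Unequal missingness separates them, in either direction:

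| dT, dP | mP | Placebo MI | Return to baseline |
|---|---|---|---|
| 15%, 35% | +3 | -10.2 | -9.6 |
| 15%, 35% | -3 | -10.2 | -10.8 |
| 30%, 20% | +3 | -8.4 | -8.7 |

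**Step 3: the responder odds ratio** (unadjusted, 25% missing per arm). Placebo MI gives 0.75 x 0.46 + 0.25 x 0.20 = 39.5% against 20%, odds ratio 2.61. Under return to baseline, let q be the share of imputed values reaching a 5% loss. The rates are then 0.345 + 0.25q and 0.15 + 0.25q:

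| q | 0% | 5% | 10% | 20% | 31% |
|---|---|---|---|---|---|
| Odds ratio | 2.98 | 2.87 | 2.77 | 2.61 | 2.48 |

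Return to baseline is therefore a different analysis here, but it is more favourable to tirzepatide than the primary unless q exceeds 20%.

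**Step 4: where the mean tips.** Add δ to imputed tirzepatide values under the fallback. The difference is -9 + 0.25δ. The shift also widens the tirzepatide arm: its variance becomes 100 + 0.25 x 0.75 x (12 + δ)². At δ = 25.7 this is 100 + 0.1875 x 37.7² = 366.5. The within-imputation variance is (366.5 + 100)/300 = 1.555. Between-imputation variance adds about 2 x 0.25² x 100/75 = 0.167. The SE is √1.722 = 1.31, and 1.96 x 1.31 = 2.57, which matches the remaining difference of -9 + 6.43 = -2.57. The tipping point is roughly 26 points.

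**Step 5: where the responder result tips.** In the worst case for a tirzepatide-only shift, every missing tirzepatide participant is a non-responder: 0.75 x 0.46 = 34.5% against 20%. The pooled rate is 27.25%, the SE is √(0.2725 x 0.7275 x 2/300) = 0.0364, and z = 0.145/0.0364 = 3.99, or about 3.8 once imputation variance is counted. It does not tip.

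**The case against.** The strongest reply is that the problem is conditional and has no shown consequence. Without the fallback, placebo multiple imputation and return to baseline both differ from the retrieved-dropout primary; only sensitivity 1 stays close, differing solely for Category 1. The protocol also works to obtain retrieved dropouts: Section 7.1 asks participants who stop drug to keep attending, Section 7.2 says stopping drug is not a reason to leave the study, and Visit 99 seeks a Week 72 weight from those who decline other visits. The sensitivity set was added after regulator feedback that we cannot see, and SAP 4.1 allows further analyses. All of this stands. It limits the point to the fallback and makes it an improvement rather than a defect in the primary inference.

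It does not remove the duplication, which follows from the wording of 4.3.2.3 and 4.3.2.4. The MMRM on the EAS does not fill the gap, because it targets the hypothetical efficacy estimand.

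A reader might infer that robustness to missing weights goes untested. The documents do not support that: return to baseline survives, generally differs on the odds ratio, and differs on the mean when missingness is unequal and the placebo mean is not zero. Nor does the SAP say that agreement among these analyses would be reported as proof of robustness.

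**Conclusion.** The point holds in a limited form. Under the fallback, one distinct sensitivity analysis is left out of three. For the mean co-primary it has the same expectation as the primary at equal missingness (-9.0 for both at 25%), and otherwise differs only by the placebo mean times the difference in missing shares. For the responder co-primary it gives an odds ratio of 2.48 to 2.98 against 2.61, so it is distinct but not necessarily stricter.

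It would be wrong to infer that the trial's conclusion is fragile. With 25% missing per arm and SD 10, the mean result tips only at roughly 26 points worse than placebo, and the responder result does not tip under a tirzepatide-only shift. Holding the SE at about 1 would give (9 - 1.96)/0.25 = 28 points, but that overlooks the variance the shift adds. These figures rest on planning values, on dropout standing in for missing Week 72 weights, and on missingness unrelated to outcome within arm before the shift. The documents do not say how likely the fallback is.

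**What to change.** In SAP 4.3.2.4:

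- Add a two-way delta-adjusted multiple imputation for both co-primaries, built on whichever imputation the primary used. Shift imputed tirzepatide and placebo Week 72 values separately, dichotomise after the shift, and report the combinations at which significance is lost, or that none exists. Shifting placebo as well is needed because, at planning values, a tirzepatide-only shift has no tipping point for responders.
- State that under the fallback sensitivity analyses 1 and 2 are identical to the primary and will not be presented as sensitivity analyses.

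Same-arm missing-at-random imputation would not be a useful replacement: it gives missing tirzepatide participants the tirzepatide mean, so the difference returns to about -12 instead of -9, which favours the drug.

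The cost is modest SAP text and a short programming task, with no new data.

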4.4. Secondary Endpoint(s) Analysis

4.4.1. Key Secondary Analyses Subject to Type 1 Error Rate Control

Table GPHM.4.2. Secondary Measures Controlled for Type 1 Error

Objectives	Relative to the Efficacy Measure	Analysis Conducted in a Manner Similar to	Additional Information
Tirzepatide MTD QW is superior to placebo from randomization for maintaining body weight reduction achieved during the 12-week lead-in period (measured at 72 weeks)	Percentage of study participants who maintain $\geq 80\%$ of the body weight lost during the 12-week lead-in period	Logistic model in Section 4.3.2.1 for treatment regimen estimand and logistic model in Section 4.3.2.2 for efficacy estimand	
Tirzepatide MTD QW is superior to placebo from randomization for body weight reduction (measured at 72 weeks)	Percentage of participants achieving body weight reduction $\geq 10\%$, $\geq 15\%$, and $\geq 20\%$ from randomization at 72 weeks	Logistic model in Section 4.3.2.1 for treatment regimen estimand and logistic model in Section 4.3.2.2 for efficacy estimand	
Tirzepatide MTD QW is superior to placebo from randomization for waist circumference reduction (measured at 72 weeks)	Mean change in waist circumference (cm) from randomization at 72 weeks	ANCOVA model in Section 4.3.2.1 for treatment regimen estimand and MMRM model in Section 4.3.2.2 for efficacy estimand	LSM estimates will be plotted by treatment through 72-weeks.

Abbreviations: ANCOVA = analysis of covariance; LSM = least squares mean; MMRM = mixed model for repeated measures; MTD = maximum tolerated dose; QW = once weekly.

Decision will be guided by the 2-sided p-values in each objective, and details will be included in Section 2.1.

For submission of Study GPHM to the US FDA to support the registration of tirzepatide for chronic weight management, the key secondary efficacy assessment will be guided by the treatment regimen estimand, conducted using the same population as the primary analysis. Assessment of the key secondary objective will be conducted with hybrid imputation of missing data (see Section 4.3.2.3).

For other regulatory agencies, publications, and other purposes, the assessment of key secondary efficacy objectives may be guided by the efficacy estimand, using the same population as the primary analysis.

4.4.2. Supportive Secondary Endpoints

Unless otherwise specified, other secondary and exploratory efficacy analyses will be guided by the efficacy estimand, using the same population as the primary analysis.

Analyses for labs will be performed for both Système International (SI) units and conventional (CN) units.

4.4.2.1. Additional Secondary Efficacy Analyses

Table GPHM.4.3. Secondary Measures Not Controlled for Type 1 Error

Objective	Relative to the Efficacy Measure	Analysis Conducted in a Manner Similar to	Additional Information
Compare tirzepatide MTD QW with placebo from randomization for body weight and BMI reduction (measured at 72 weeks)	Mean change in body weight (kg) from randomization	MMRM model in Section 4.3.2.2	LSM estimates through 72 weeks will be plotted by study treatment.
	Mean change in BMI (kg/m ²) from randomization	MMRM model in Section 4.3.2.2	LSM estimates through 72 weeks will be plotted by study treatment.
Compare tirzepatide MTD QW with placebo from randomization for blood pressure reduction (measured at 72 weeks)	Mean change in systolic blood pressure (mmHg)	MMRM model in Section 4.3.2.2	LSM estimates through 72 weeks will be plotted by study treatment.
	Mean change in diastolic blood pressure (mmHg)	MMRM model in Section 4.3.2.2	LSM estimates through 72 weeks will be plotted by study treatment.
Compare tirzepatide MTD QW with placebo from randomization for improvement in lipid parameters (measured at 72 weeks)	Mean change in total cholesterol, HDL-C, non-HDL-C, LDL-C, VLDL-C, triglycerides, and free fatty acids from randomization	MMRM model in Section 4.3.2.2	Estimated means through 72 weeks will be plotted by study treatment. Log transformation will be adopted for lipid parameters.

Objective	Relative to the Efficacy Measure	Analysis Conducted in a Manner Similar to	Additional Information
Compare tirzepatide MTD QW with placebo from randomization for improvement of glycemic control (measured at 72 weeks)	Mean change in fasting glucose from randomization	MMRM model in Section 4.3.2.2	LSM estimates through 72 weeks will be plotted by study treatment.
	Mean change in HbA1c from randomization	MMRM model in Section 4.3.2.2	LSM estimates through 72 weeks will be plotted by study treatment.
Compare tirzepatide MTD QW with placebo from randomization for insulin reduction (measured at 72 weeks)	Mean change in fasting insulin	MMRM model in Section 4.3.2.2	Estimated means through 72 weeks will be plotted by study treatment. Log transformation will be adopted for fasting insulin.
Compare tirzepatide MTD QW with placebo from randomization for improvement of patient-reported outcomes (measured at 72 weeks)	Mean change in SF-36v2 acute form Physical Functioning (PF) domain score from randomization	ANCOVA model	Use terms of treatment, stratification factors, and baseline SF-36v2 PF score as a covariate. Missing data will be imputed using LOCF.
Compare tirzepatide MTD QW with placebo from randomization for improvement of patient-reported outcomes (measured at 72 weeks)	Mean change in IWQOL-Lite-CT PF composite score from randomization	ANCOVA model	Use terms of treatment, stratification factors, and baseline IWQOL-Lite-CT PF score as a covariate. Missing data will be imputed using LOCF.
Compare tirzepatide MTD QW with placebo from Visit 2 for body weight and BMI reduction (measured at 72 weeks)	Mean change in absolute body weight (kg) from Visit 2	MMRM model in Section 4.3.2.2 with body weight at Visit 10 (Week 0) as an additional covariate	LSM estimates through 72 weeks will be plotted by study treatment.
	Mean percent change in body weight from Visit 2	MMRM model in Section 4.3.2.2 with body weight at Visit 10 (Week 0) as an additional covariate	
	Mean change in BMI (kg/m ²) from Visit 2	MMRM model in Section 4.3.2.2 with body weight at Visit 10 (Week 0) as an additional covariate	LSM estimates through 72 weeks will be plotted by study treatment.

Objective	Relative to the Efficacy Measure	Analysis Conducted in a Manner Similar to	Additional Information
Compare tirzepatide MTD QW with placebo from Visit 2 for waist circumference reduction (measured at 72 weeks)	Mean change in waist circumference (cm)	MMRM model in Section 4.3.2.2	LSM estimates through 72 weeks will be plotted by study treatment.

Abbreviations: ANCOVA = analysis of covariance; BMI = body mass index; HbA1c = hemoglobin A1c; HDL-C = high-density lipoprotein cholesterol; IWQOL-Lite-CT = Impact of Weight on Quality of Life-Lite-Clinical Trials Version; LDL-C = low-density lipoprotein cholesterol; LOCF = last observation carried forward; LSM = least squares mean; MMRM = mixed model for repeated measures; QW = once weekly; SF-36v2 = Short Form 36 version 2 Health Survey; VLDL-C = very low-density lipoprotein cholesterol.

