**4.1.1.2.4. *Early Discontinuation of Treatment Visit***

Participants unable or unwilling to continue the study intensive lifestyle intervention (during lead-in period) or study drug intervention (during treatment period) for any reason will perform an early discontinuation (ED) visit (Section 7.2.1). If the participant is discontinuing during an unscheduled visit or a scheduled visit, that visit should be performed as an ED visit. Procedures should be completed according to the SoA. Patient-reported outcomes questionnaires should be administered as early as possible, as per Suggested Visit Structure (Section 10.8). Administration of Mental Health questionnaires should follow assessment of AEs.

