- Treatment condition of interest - Tirzepatide MTD versus placebo, excluding data after discontinuation of study drug.
- Handling of ICEs - The ICEs leading to treatment discontinuation for any reason are addressed by the treatment condition of interest attribute and handled by the hypothetical strategy as described in the ICH E9 (R1) Addendum.
- Population-level summary - Difference in mean changes between treatment conditions AND difference in response percentage between treatment conditions as assessed by odds ratio.

Rationale for Estimand

The estimand aims to reflect treatment efficacy in an envisaged scenario in which the ICEs leading to treatment discontinuation would not occur.

This estimand is referred to as the “efficacy” estimand in the latter sections.

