1.1.2.2. Estimands for Secondary Endpoints

Table GPHM.1.2. Attribute Description of Estimands for Secondary Endpoints

Estimand for Secondary Endpoints	Population	Endpoint	Treatment Condition of Interest	Handling of Intercurrent Events	Population-Level Summary
Key secondary related to mean change	Same as estimands for co-primary endpoints	As described in Table GPHM.1.1	For submission to the US FDA, follow the same manner of the treatment regimen estimand in Section 1.1.2.1 ; for all other purposes, the same manner of the efficacy estimand in Section 1.1.2.1	For submission to the US FDA, follow the same manner of the treatment regimen estimand in Section 1.1.2.1 ; for all other purposes, follow the same manner of the efficacy estimand in Section 1.1.2.1	Difference in mean changes between treatment conditions
Key secondary related to percentage of participants meeting certain criteria					Difference in percentage of participants between treatment conditions
Other secondary related to mean change	Same as estimands for co-primary endpoints	As described in Table GPHM.1.1	Follow the same manner of the efficacy estimand in Section 1.1.2.1	Follow the same manner of the efficacy estimand in Section 1.1.2.1	Difference in mean changes between treatment conditions

Note: Unless otherwise specified, the attributes of estimands for supporting exploratory objectives will follow the same manner of the efficacy estimand in [Section 1.1.2.1](#).

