For the primary and key secondary efficacy endpoint analyses subject to type 1 error rate control, data for participants with missing values at the 72-week visit will be imputed based on the method described in Section 4.3.2.3. Otherwise, missing values will not be explicitly imputed except for the parameters with only 1 postbaseline measure during the analysis period per the schedule of activity, where the last-observation-carried-forward (LOCF) approach will be applied to impute the endpoint when ED measure is available.

End of study participation for a participant will be the earliest of date of death, date of withdrawal from further participation in the study, or date of safety follow-up visit (Visit 801). For participants considered to be lost to follow-up, end of study participation will be the date of lost to follow-up reported by the investigator. Participant data included in the database after the last date of study participation will be excluded from statistical analysis.

Statistical summaries and results of statistical analyses will be displayed in the following order: Placebo, tirzepatide MTD.

Not all analyses described in this SAP will necessarily be included in the clinical study reports (CSRs). Any analysis described in this SAP and not provided in the CSR would be available upon request. Not all displays will necessarily be created as a “static” display. Some may be incorporated into interactive display tools instead of or in addition to a static display.

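### Carrying the early-discontinuation score forward for the SF-36v2 and IWQOL-Lite-CT physical-function endpoints meets the SAP's hypothetical efficacy estimand only if scores would not have changed after that visit

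*SAP*

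**What the plan says.** - **Method.** SAP 4.4.2.1, Table GPHM.4.3, analyses both physical-function scores by ANCOVA with treatment, stratification factors and baseline score, and adds "Missing data will be imputed using LOCF". Table GPHM.4.4 (SAP 4.5) repeats LOCF for the exploratory questionnaire comparisons between arms.
- **What is carried forward, and why.** The reason is in SAP 4.1, which rules out explicit imputation outside the error-controlled endpoints "except for the parameters with only 1 postbaseline measure during the analysis period per the schedule of activity". For that one group of parameters, the same sentence goes on to name the ED visit as the source of the carried value: "where the last-observation-carried-forward (LOCF) approach will be applied to impute the endpoint when ED measure is available". Protocol 4.1.1.2.4 provides for the questionnaires at the ED visit: "Patient-reported outcomes questionnaires should be administered as early as possible".
- **Target.** Table GPHM.1.2 (SAP 1.1.2.2) has other secondary mean-change endpoints "follow the same manner of the efficacy estimand". SAP 4.4.2 agrees: "other secondary and exploratory efficacy analyses will be guided by the efficacy estimand". SAP 1.1.2.1 gives that estimand the hypothetical strategy, describing "an envisaged scenario in which the ICEs leading to treatment discontinuation would not occur".
- **Data set.** SAP 4.7.1 puts the questionnaires on the Efficacy Analysis Set (EAS), which excludes data later than 7 days after the last dose (Table GPHM.3.1).
- **Safeguards elsewhere.** Rubin's rules (4.3.2.1), hybrid imputation (4.3.2.3) and the imputation sensitivity analyses (4.3.2.4) serve the primary or error-controlled endpoints. None is specified for missing questionnaire scores.

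**The concern.** The estimand concerns the Week 72 score in a world without discontinuation. The ED score describes the participant at the time of stopping. The two agree on average only if the score would have stayed put from the ED visit to Week 72. If scores would have kept improving on treatment, the estimated effect depends on how many participants stop in each arm and how far they had got by then.

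There is a second, smaller issue. LOCF is a single imputation, so the ANCOVA counts carried scores as observed Week 72 scores. Its standard error takes no account of not knowing what those scores would have been.

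At stake is the size of the reported benefit on physical function, and its interval if read as the efficacy estimand. The analyses restricted to participants with limited physical function at baseline (SAP 4.7.1.2 and 4.7.1.3) inherit the same rule.

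**Working it through.** **Inputs from the documents.** 300 per arm and 25% dropout (SAP section 5). The 25% is a sizing assumption for body weight. It stands in here for the share of each arm whose score is carried forward. The SAP states no power, effect size or missing-data rate for either questionnaire.

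**The plan's own figure.** With 300 × 0.75 = 225 evaluable per arm, power is above 0.9999 for a 12-point weight difference with SD 10, and 0.99998 for 20% versus 46% responders. The stated power above 90% is reproduced; it does not bear on the questionnaires.

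**Assumed inputs.** True Week 72 changes m: 4 points on tirzepatide and 1 on placebo, a difference of 3. Share carried forward: d. Fraction of the Week 72 change reached by the ED visit: f, unknown.

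**Formula.** LOCF mean per arm = m × [(1 − d) + d × f] = m × [1 − d(1 − f)].

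**Equal dropout, d = 25%, every dropout with a usable ED score.**
- f = 0.3: 3 × (1 − 0.25 × 0.7) = 3 × 0.825 = 2.475, a 17.5% loss.
- f = 0.5: 3 × (1 − 0.25 × 0.5) = 3 × 0.875 = 2.625, a 12.5% loss.

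Share of the true difference retained over a wider range:

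| d | f = 0.2 | f = 0.5 | f = 0.8 | f = 1.0 |
|---|---|---|---|---|
| 10% | 0.92 | 0.95 | 0.98 | 1.00 |
| 25% | 0.80 | 0.875 | 0.95 | 1.00 |

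**Only half the dropouts with a usable ED score.** If the others are left out, as SAP 4.1 implies, the carried share among those analysed is 0.125/0.875 = 1/7. The loss is 1/7 × 0.7 = 10% at f = 0.3 and 1/7 × 0.5 = 7% at f = 0.5.

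**Unequal dropout.** Bias = −(1 − f) × (d_T × m_T − d_P × m_P), with T for tirzepatide and P for placebo.
- 30% tirzepatide, 20% placebo, f = 0.3: 4 × 0.79 − 1 × 0.86 = 3.16 − 0.86 = 2.30, a 23% loss.
- The sign turns in favour of tirzepatide when d_P × m_P exceeds d_T × m_T. With changes of 4 and 1, placebo dropout would have to be more than four times the tirzepatide dropout. With similar changes in both arms, a small imbalance is enough.
- No true effect, a common 0.5 SD improvement, 30% placebo and 20% tirzepatide dropout, f = 0.2: bias = 0.5 × 0.8 × 0.10 = 0.04 SD in favour of tirzepatide.

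**Interval.** I simulated the ANCOVA: 3,000 runs, 300 per arm, dropout at random, correlation 0.5 between baseline and each later score, and 0.6 between ED and Week 72 scores. The true effect was 0.3 SD with d = 25%.
- Coverage of the hypothetical effect by the 95% interval was 86%, 91%, 94% and 95% at f = 0.2, 0.5, 0.8 and 1.0.
- The LOCF model standard error was 0.071, against 0.082 from the 225 observed scores per arm. The ratio of about 0.87 is √(225/300).
- The empirical spread of the LOCF estimate was also about 0.071.
- In the no-effect case above, two-sided rejection was 8.8% at f = 0.2 and 5.5% at f = 0.8. With 35% placebo and 15% tirzepatide dropout it was 19.3% and 5.2%.

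**The case against.** The strongest defence is that the SAP gives its reason. These parameters have one scheduled postbaseline measure, so the repeated-measures model used for body weight is not available. That stands, but it does not lead to LOCF. On-drug weight is measured repeatedly and can inform an imputation model.

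Several stronger readings are tempting, and the documents do not support them:

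- **That the confidence interval is simply invalid.** The standard error is right for the LOCF contrast itself. It is too small only when read as the precision of the hypothetical Week 72 effect. In the simulation, coverage was lost through bias and was nominal at f = 1.
- **That ED scores mostly come early in escalation or during an adverse event.** Escalation takes 20 of 72 weeks (Protocol 4.1). Protocol 7.1 also lists participant decision as a reason for stopping, and Protocol 6.6.2 foresees gastrointestinal discontinuation after Week 24. The timing is unknown.
- **That LOCF is reliably conservative.** It attenuates a growing benefit when dropout is equal, but the direction is not assured otherwise.
- **That the body-weight analyses of this estimand avoid single imputation.** The MMRM for mean change does. The efficacy-estimand responder analysis (SAP 4.3.2.2) fills each missing weight with one predicted value and then dichotomizes.
- **That the trial's main conclusions are exposed.** SAP 2.1 and the title of Table GPHM.4.3 place these endpoints outside type 1 error control.

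**Conclusion.** The mismatch holds. For both physical-function endpoints, the estimator targets the score at discontinuation, while the stated estimand concerns Week 72 without discontinuation. They coincide only under an assumption of no later change, which the SAP leaves unstated and untested.

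With 25% carried forward in each arm and 30-50% of the change reached, the loss is 12.5-17.5% of the difference. It falls to 7-10% if half the dropouts have a usable ED score, and to nothing at f = 1. Only the 25% comes from the SAP; the changes, f and the dropout splits are assumptions, so these figures show scale and are not predictions.

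The carry-forward rule is also incomplete. Table GPHM.4.3 applies LOCF without condition, while SAP 4.1 requires an ED measure. An ED score taken more than 7 days after the last dose falls outside the EAS. The SAP does not say whether such a score, or the baseline score when no ED score exists, is carried forward.

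The point is minor: the endpoints are supportive, and the sample size and the primary and key secondary conclusions are untouched.

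**What to change.** In Tables GPHM.4.3 and GPHM.4.4, replace LOCF as the main method with multiple imputation of the Week 72 score, under missing at random within arm, from on-drug (EAS) participants.

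1. Impute missing on-drug body weights through Week 72.
2. Impute the score from baseline score and visit-matched weights. Weight change to the last on-drug visit will not do: it means Week 72 in completers and an earlier time in those who stopped.
3. Do not use the ED score as a predictor. No on-drug completer has one, so its relation to an on-drug Week 72 score cannot be estimated.
4. Pool with Rubin's rules.
5. Keep LOCF as a sensitivity analysis. State whether ED scores taken more than 7 days after the last dose are used, and what is done when there is no ED score.

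Alternatively, keep LOCF and declare for these endpoints an intercurrent-event strategy that it does estimate.

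The cost is SAP wording and modest programming, somewhat more than a one-step imputation because weight comes first. The method relies on missing at random, as the efficacy-estimand MMRM already does. No new data are needed.
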